	11.1 Definitions	
	11.1.1 Adverse Events (AEs)	
	11.1.2 Common Treatment Responses (CTRs)	
	11.1.3 Serious Adverse Events and Unexpected Adverse Device Effects	23

	11.1.4	Severity	23	
	11.1.5	Relationship to Study Device	23	
	11.2	Procedures for Reporting Adverse Events	23	
		Procedures for Unmasking of Study Devices		
	11.4	Pregnancy	24	
12.	STATIS	TICS		24
	12.1	Sample Size Justification	24	
	12.2	Efficacy Parameter Analysis	24	
		Safety Analysis		
13.	ADMINI	STRATIVE ISSUES		25
		Protection of Human Subjects		
	13.1.1	•		25
	13.1.2			
	13.1.3			
	13.2	Changes to the Protocol	25	
	13.3	Subject Confidentiality and Privacy	25	
	13.4	Required Regulatory Documents	26	
	13.4.1			
	13.4.2	! Electronic Case Report Form (eCRF) Completion	26	
	13.4.3			
	13.4.4	Retention of Documentation	27	
		Monitoring by the Sponsor		
		On-Site Audits		
		Proprietary Information		
		Publications	27	
	13.9	References	28	
APP	ENDIX 1	STUDY ASSESSMENTS		30
APP	ENDIX 2	: MICRONEEDLING PROCEDURE		32
APP	ENDIX 3	SKIN TEST INSTRUCTIONS FOR USE		34
APP	FNDIX 4	BELLAFILL INSTRUCTIONS FOR USE		40

GLOSSARY OF ABBREVIATIONS

AE	Adverse Event	
ASAS	Acne Scar Assessment Scale	
CFR	U. S. Code of Federal Regulations	
eCRF	Electronic Case Report Form	
CRO	Contract Research Organization	
CTR	Common Treatment Responses	
FDA	Food and Drug Administration	
GCP	Good Clinical Practices	
HIPAA	Health Insurance Portability and Accountability Act	
ICF	Informed Consent Form	
ICH	International Conference on Harmonization	
IRB	Independent Review Board	
ITT	Intent to Treat	
NSAID	Non-steroidal anti-inflammatory drug	
PGAIS	Physician Global Aesthetic Improvement Scale	
PMMA	Polymethylmethacrylate	
QoL	Quality of Life	
SAE	Serious Adverse Event	
SAS	Statistical Analysis Software	
SDs	Source Documents	
SGAIS	Subject Global Aesthetic Improvement Scale	
UADE	Unanticipated Adverse Device Effects	
UPT	Urine Pregnancy Test	
WOCBP	Women of Child Bearing Potential	

PROTOCOL SYNOPSIS

A Pilot Study to Evaluate the Safety and Effectiveness of Microneedling and Bellafill® to Treat Facial Acne Scars				
Bellafill [®]				
To evaluate the effectiveness and safety of atrophic acne scar treatment that sequentially employs microneedling followed by Bellafill injections.				
Male and female subjects \geq 21 years of age with \geq 4 distensible atrophic acne scars located in the facial area that, in the Investigator's opinion, are correctable.				
Open-label, randomized, multicenter, prospective pilot study.				
Approximately 9 sites.				
Approximately 45 subjects.				
Group A: Microneedling and Bellafill.				
Group B: Microneedling.				
The duration of the study is approximately 12 months.				
 Outpatient, male or female subjects of any race, 21 years of age or older. Female subjects of childbearing potential must have a negative urine pregnancy test result at Baseline and practice a reliable method of contraception throughout the study. Negative response to the Bellafill Skin Test. Presence of ≥4 distensible atrophic acne scars (treatment scars) in the facial area. Subjects with a history of HSV-1 (oral herpetic outbreak) willing to accept prophylactic treatment with antiviral medication. Subject desires correction of his/her atrophic acne scarring. All Fitzpatrick skin types are eligible. Willing to withhold additional aesthetic therapies to the proposed treatment area (e.g., other soft tissue fillers such as hyaluronic acid, and/or any resurfacing procedures (as described in Protocol Section 5.3) for the duration of the study. Able to follow study instructions and likely to complete all required visits, as assessed by the Investigator. Sign an IRB-approved Informed Consent Form, Photographic Release Form, and the Authorization for Use and release of Health and Research Study Information (HIPAA) Form prior to any study-related procedures being performed. 				
 Female subjects that are pregnant (positive urine pregnancy test), breast-feeding, or who are of childbearing potential and not practicing a reliable method of birth control. Undergone facial treatments with any prohibited treatment/procedures and/or use of any other prohibited treatment/procedure within certain time periods as listed in Protocol Section 5.3. Excisional facial surgery (such as Blepharoplasty, Face Lift, Rhinoplasty) of the face ≤ 6 months prior to study enrollment or plans for facial surgery 				

- during the study.
- 4. History of bleeding disorders.
- 5. Presence of any skin pathology or condition that could interfere with the evaluation of the treatment areas, worsen due to the proposed treatment or require interfering topical, systemic or surgical therapy.
- 6. Recent or current history of inflammatory skin disease, infection, cancerous/pre-cancerous lesion, unhealed wound or clinically significant acne in the proposed treatment areas. Clinically significant acne is defined as a patient whom has ≥3 active inflammatory acne lesions in the treatment areas.
- 7. History of systemic granulomatous diseases active or inactive (e.g., Sarcoid, Wegeners, TB) or connective tissue diseases (e.g., lupus, dermatomyositis).
- 8. Hypertrophic acne scars, any evidence of keloid scarring in the treatment area.
- 9. Known hypersensitivity or previous allergic reaction to any of the components of the study device (including lidocaine or any amide-based anesthetic), or has a history of allergies to any bovine collagen products, including but not limited to injectable collagen, collagen implants, hemostatic sponges, and collagen-based sutures.
- 10. Undergone or be planning to undergo desensitization injections to meat products.
- 11. Unable to communicate or cooperate with the Investigator due to a language barrier (non-English speaking), poor mental development, or impaired cerebral function.
- 12. Evidence of alcohol or drug abuse (Investigator opinion), or history of poor cooperation, non-compliance with medical treatment, or unreliability.
- 13. Use of an investigational device, biologic or drug in the past 30 days, or be currently participating in an experimental drug, biologic or device trial.
- 14. Exhibits additional physical attributes which prevent the assessment or treatment of the atrophic scars, as judged by the Investigator, such as excessive hair, traumatic or surgical scars, excessive hyperpigmentation in the treatment area, etc.
- 15. Has a condition or be in a situation that, in the Investigator's opinion, may put the subject at significant risk, may confound the study results, or may interfere significantly with the subject's participation in the study.
- 16. An employee (or a relative of an employee) of the Investigator, Sponsor or representative of the Sponsor.

Study Measurements

Effectiveness:

- Acne Scar Assessment Scale (ASAS): a validated 5-point static scale assessing physician impression of acne scar severity.
- Physician Global Aesthetic Improvement Scale (PGAIS): a 5-point dynamic scale assessing cosmetic improvement.
- Subject Global Aesthetic Improvement Scale (SGAIS): a 5-point dynamic scale assessing cosmetic improvement.
- Subject QOL Impact Scale: (33 questions): a 33-question survey that allows the subject to specifically address how acne scarring has affected his/her emotional and functional status.

Safety:

• Adverse events: rate of AEs, type of AEs, relationship of AEs to Bellafill.

Study The study is divided into two study Periods. In **Period I**, subjects will attend a **Procedures** Screening visit (Week -4) and undergo the Bellafill skin test. At Visit 1 (Day 0), all subjects will commence microneedling treatment for their atrophic acne scars. Subjects will then return to the clinic at Week 3 and Week 6 (Visits 2 and 3, respectively) for follow-up evaluation and additional cycles of microneedling treatment. At Week 12 (Visit 4), all subjects commence **Period II** and are randomized to Bellafill Treatment (Track A) or to No Treatment (Track B): Track A: Consists of three (3) study visits. At Visit 4, subjects randomized to the "Bellafill" group will complete visit evaluations and then receive treatment with Bellafill for their atrophic acne scars. Subjects return for Visit 5A (Month 1 after randomization) for evaluation and followup, and will receive touch-up injections with Bellafill to achieve optimal correction (if necessary). Subjects will then be followed-up at Visits 6A and 7A which will occur at Month 3 and Month 6, respectively, after their last Bellafill treatment. Track B: Consists of one (1) study visit. At Visit 4, subjects randomized to the "No Treatment" group will complete visit evaluations and then return for follow-up at Visit 5B (approx. Month 3 after randomization). This is a pilot study and a formal sample size justification is not provided. It is Sample Size the opinion of the Sponsor that a total of 45 subjects will be sufficient to Justification achieve the objectives of the study. Statistical analyses will be conducted on an ITT basis (i.e., all enrolled Statistical subjects that have fully passed screening and have received initial Methods microneedling treatment will be included in the analyses). Descriptive statistics (i.e., mean, standard deviation, etc.) will be provided for all continuous variables and frequencies for all categorical variables collected in this study. When appropriate, exploratory inferential statistical analyses will be conducted using SAS® software (9.3 or higher). Comparisons between treatment groups will be performed using parametric or non-parametric testing, as appropriate. The level of significance will be fixed at 0.05. No adjustments for multiplicity will be performed.

1. Background and Rationale

Acne scars occur when acne lesions become large enough that the amount of localized inflammation overcomes the skin's ability to heal normally. Dermal collagen is damaged and resorbed, leaving defects that are manifested as concavities in the skin surface.. There are two general categories of Acne Scars; **atrophic or depressed** (depressions and valleys in the skin with resulting shadowing), and **hypertrophic or raised** (firm, raised papules or nodules on the skin).¹

Typically, over 90% of the U.S. population experiences the onset of acne during puberty and teen years² with some women experiencing episodes in the late 20's through their 40's due to hormonal changes.³ A significant percentage will go on to have long term or extensive acne scarring,¹ 90% of which are atrophic acne scars and the remaining 10% hypertrophic or some mix of both scars.⁴ The most commonly used descriptors for atrophic scars fall into the following categories.⁵

- *Ice Pick* Deep, narrow sharply marginated scars which resemble how the skin might look if injured with an ice pick.
- Rolling or Distensible More superficial scars with rolled edges that blend more gently
 into surrounding normal skin.
- Boxcar Sharply marginated depressions with a flat bottom, broader than Ice Pick scars.

1.1 Incidence and Severity of Acne Scarring

There is no definitive source of data that clearly shows how many people are afflicted with each type of scar in the U.S. However, based on the few published studies found in the peer-reviewed literature and following discussions with our clinical advisors, Suneva Medical Inc. has developed a general picture of how many people are afflicted.

With regard to scar type, between 60 to 75% of the people with acne scars will have a form of rolling or distensible scar as their predominant scar type with roughly 5 to 10% having mostly boxcar scars. The remaining 15 to 20% will have ice pick scars as their most common scar finding.⁶ Most individuals with acne scarring will have a mixture of two or more types of depressed scars.

Severity is challenging to define due to irregularities in the scar depression and the large range in the shape and size of acne scars. In general, studies suggest that mild scarring occurs in roughly 60 to 70% of people with scars, moderate scarring occurs in 15 to 25% and 5 to 15% of people with scars suffer from severe scarring.⁷

1.2 Treatment of Acne Scarring with Bellafill

Bellafill has been proven to be safe and effective in improving the appearance of atrophic acne scars by raising the base of the scar so that it is level with the surrounding skin. Based on a pivotal double-blinded, randomized, placebo-controlled study, the FDA approved Bellafill for the correction of acne scars in December 2014.

The study required a high threshold for success in which the primary effectiveness endpoint was proven superior for subjects treated with Bellafill compared to Control at 6 months. At 6 months, the response rate for Bellafill was 64% vs. 33% for Control (p=0.0005). Bellafill continued to show effectiveness by an unblinded assessment at 12 months (71%). A responder was defined as a subject in whom \geq 50% of treated acne scars improved by \geq 2 points on the validated 4-point Acne Scar Rating Scale (ASRS).

On the Physician Global Aesthetic Improvement Scale (PGAIS), 84% of subjects were rated as improved at 6 months and 98% were improved at 12 months by an unblinded assessment. On the Subject Global Aesthetic Improvement Scale (SGAIS), 77% of subjects rated their appearance as improved at 6 months and 83% rated their appearance as improved at 12 months.

1.3 Microneedling for the Correction of Acne Scarring

Microneedling involves puncturing the skin with fine, sterile needles to create small wounds in the dermis that is thought to stimulate wound healing resulting in collagen production. A mechanical device, consisting of steel microneedles in a wheel, is rolled over the surface of the skin in a patterned formation. The microneedles penetrate approximately 0.25 to 3.0 millimeters below the skins surface, and each puncture creates a channel that triggers production of new collagen and elastin, leading to improvement in the appearance of skin texture, firmness, and acne scarring. While microneedling is a popular and common procedure practice in many dermatological clinics, it has not been approved by the FDA as a treatment for acne scarring.

1.4 Current Clinical Study

A therapy that may stimulate collagen production, such as microneedling, is potentially a useful adjunct to atrophic acne scar treatment with Bellafill. The current pilot study will evaluate the effectiveness and safety of sequential treatment of microneedling followed by intra-scar injections with Bellafill.

2. Study Objective

To evaluate the effectiveness and safety of acne scar treatment that sequentially employs microneedling followed by Bellafill injections.

3. Study Design

[figure not shown]
This is an open-label, randomized, multicenter, prospective trial assessing the efficacy and safety of microneedling treatment alone vs. microneedling treatment followed by treatment with Bellafill for correction of distensible atrophic facial acne scars.

The study is divided into two study Periods. In **Period I**, subjects will attend a Screening visit (Week -4) and undergo the Bellafill skin test. At Visit 1 (Day 0), all subjects will commence microneedling treatment for their atrophic acne scars. Subjects will then return to the clinic at Week 3 and Week 6 (Visits 2 and 3, respectively) for follow-up evaluation and additional cycles of microneedling treatment.

At Week 12 (Visit 4), all subjects commence **Period II** and are randomized to Bellafill Treatment (Track A) or to No Treatment (Track B):

- Track A: Consists of three (3) study visits. At Visit 4, subjects randomized to the "Bellafill" group will receive treatment with Bellafill for their atrophic acne scars. Subjects return for Visit 5A (Month 1 after randomization) for evaluation and follow-up, and will receive touch-up injections with Bellafill to achieve optimal correction (if necessary). Subjects will then be followed-up at Visits 6A and 7A which will occur at Month 3 and Month 6, respectively, after their last Bellafill treatment.
- **Track B:** Consists of one (1) study visit. At Visit 4, subjects randomized to the "No Treatment" group will complete visit evaluations and then return for follow-up at Visit 5B (approx. Month 3 after randomization).

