8.1 Photography

Facial photography will also be employed in this study. Baseline photographs will be used for PGAIS and SGAIS assessments. Canfield Scientific Inc. will provide each site with photographic equipment, training and an Instruction Manual prior to the start of the study.

9. Safety Assessments

Throughout the study, subjects will be instructed to report any unusual signs or symptoms to the Investigator.

The Investigator will solicit and record information about AEs, and concomitant medications, therapies and treatments. At each post-treatment visit, phone call, or email contact, the Investigator (or designee) will begin by asking the subject a general, non-directed question such as 'How have you been feeling since the last visit?' Directed questioning and examination will then be done as appropriate. All reported AEs will be documented in the eCRF.

10. Schedule of Study Activities

Subjects must have a negative Bellafill skin test prior to receiving study treatment. Additionally, a negative screening urine pregnancy test is required for women of childbearing potential. Please refer to the following assessment schedule for additional details:

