10.1 Assessment Schedule

								Pe	riod II	
Period I			Track A Bellafill			Track B No-Tx				
	Visit	Screening	1	2	3	4	5a	6a	7a	5b
	1 week = 7D 1 month = 28D	W -4	D0	W3 ±3D	W6 ±3D	W12 ±1W	M1 ±1W	M3 [†] ±1W	M6 [†] ±1W	M3 ^{††} ±1W
Inf	ormed Consent	Х								
Inc	l/Excl Criteria, Med Hx	Х	X confirm							
UF	PT (if applicable)	Х	X ¹			X ¹	X ¹			
Fa	cial Scar Photography	Х				X ¹			Х	Х
Ве	llafill Skin Test	X Placement	X Reading							
Microneedling Treatment			Х	Χ	Х					
Ra	ndomization					R				
Bellafill Injections Initial injection Touch-up						l²	T ³			
ş	ASAS (Investigator)	Х						Χ	Х	Χ
nen	PGAIS (Investigator)					X ¹		Х	Х	Х
PGAIS (Investigator) SGAIS (subject) QoL Scar Impact Scale						X ¹		Χ	X	Χ
Ass	QoL Scar Impact Scale (subject)		X ¹						Х	Х
Со	n Meds/Procedures	X	Χ	Χ	Χ	Х	Χ	Χ	Х	Χ
Ad	verse Events	Х	Х	Χ	Χ	Χ	Χ	Χ	Χ	Х

[†] Visits to occur 3M and 6M after last injection of Bellafill (i.e., initial treatment or touch-up treatment)

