10.3 Study Period II (Track A – Bellafill Treatment)

10.3.1 Visit 5a (M1 ± 1W)

The following activities will be conducted 1M from Visit 4:

- UPT (if applicable)
- Concomitant Medication/Procedures and AE assessment

Touch-up Study Treatment

- The Investigator will examine the subject and determine if touch-up treatment is required to achieve optimal correction. Previously treated scars determined to be undercorrected will receive touch-up treatment. New scars (i.e., previously untreated) may not be treated.
- Document the number of scars treated as well as the method and volume of treatment.
- Subjects who merit additional treatment but decline touch-up treatment will not be retreated but will continue to participate in the study if they otherwise consent to continued participation.

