10.4 Study Period II (Track B – No Treatment)

10.4.1 Visit 5b (M3 ± 1W)

The following activities will be conducted 24W from Visit 1:

- Concomitant Medication/Procedures and AE assessment
- Facial Scar Photography
- ASAS and PGAIS
 - The Investigator will refer to Baseline photographs for PGAIS evaluation.
- QoL Scar Impact Scale and SGAIS
 - The subject will refer to Baseline photographs for SGAIS evaluation.
- Study Exit

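### Track A has a scheduled adverse-event assessment one month after randomisation and Track B has none until about Week 12, so short, unreported events may be under-ascertained in Track B

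*Combined protocol and SAP*

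**What the plan says.** - **Aim.** Section 3 describes the trial as assessing "efficacy and safety of microneedling treatment alone vs. microneedling treatment followed by treatment with Bellafill", so a between-track view of safety is part of the stated design.
- **Visits after randomisation.** In Section 3, Track A "Consists of three (3) study visits" (5a, 6a, 7a) and Track B "Consists of one (1) study visit" (5b).
- **Track A, Month 1.** Section 10.3.1 opens "The following activities will be conducted 1M from Visit 4" and lists "Concomitant Medication/Procedures and AE assessment".
- **Track B.** Section 10.4.1 opens "The following activities will be conducted 24W from Visit 1". The schedule in 10.1 and the Visit 4 instructions in 10.2.4 place this at roughly three months after Visit 4. No Track B contact is scheduled in between.
- **How AEs are found.** Section 9: "At each post-treatment visit, phone call, or email contact, the Investigator (or designee) will begin by asking the subject" a general question, with directed questions to follow. Telephone and e-mail contacts are mentioned, but none is scheduled. Subjects in both tracks are also told to report symptoms themselves (Sections 9 and 10.5), and AEs are solicited at unscheduled visits (10.6).
- **Timing of 6a.** Section 10.3.2 counts three months from Visit 4. The synopsis, Section 3, the note to Section 3.1 and the footnote to 10.1 count from the last Bellafill injection, touch-up included.
- **Analysis.** Section 12.3 plans AE tabulations and a listing. It gives no between-track test, common time window or exposure adjustment.

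**The concern.** A mild event that has resolved within days is often recorded only if someone asks about it soon enough. Every Track A subject is asked at about Week 4. A Track B subject has no scheduled question for about 12 weeks. An event in the first month after randomisation then waits 0-4 weeks for a question in Track A and 8-12 weeks in Track B.

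This differs from Track A's longer total follow-up. Cutting both tracks at Week 12 removes the extra follow-up but leaves the unequal asking. If short events fade from memory, the control incidence comes out too low and the apparent Bellafill excess too high. Concomitant treatments are elicited at the same contacts. That matters for Track B in particular: Section 4.2 recruits people who want filler correction, and Section 5.3 treats use of prohibited therapies as protocol deviations.

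**Working it through.** **Timing (from the documents).** The schedule sets "1 week = 7D 1 month = 28D".

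- 5b: 24 − 12 = 12 weeks after Visit 4, and 3 × 28 days = 12 weeks, so the plan's own equivalence reproduces. With the visit windows it is 23 − 13 = 10 to 25 − 11 = 14 weeks.
- 5a: Week 4.
- 6a without touch-up: Week 12. After a Month 1 touch-up, counted from the last injection: 4 + 12 = Week 16. Counted from Visit 4 (10.3.2): Week 12 for all.

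**Mean wait from onset to the next scheduled AE question**, for onset spread evenly over Weeks 0-12 (assumption):

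| Group | Asked at weeks | Onset 0-4 | Onset 4-12 | Overall |
|---|---|---|---|---|
| Track A, no touch-up | 4, 12 | 2 | 4 | (4×2 + 8×4)/12 = 3.33 |
| Track A, touch-up, last-injection rule | 4, 16 | 2 | 8 | (4×2 + 8×8)/12 = 6.0 |
| Track B | 12 | 10 | 4 | (4×10 + 8×4)/12 = 6.0 |

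Without touch-up, the whole difference from Track B arises in Weeks 0-4. With touch-up, Track A waits less in Weeks 0-4 and longer in Weeks 4-12. Its waits cover 0-4 and then 4-12 weeks, which is the same 0-12 spread as Track B's.

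**Illustrative recall model.** The documents give no recall figure, so the half-life h (weeks) is assumed. Mean capture over an interval of L weeks that ends in a question is f(L) = (1 − 2^(−L/h)) / ((L/h) × ln 2). Track A without touch-up captures (4·f(4) + 8·f(8))/12. Track B captures f(12), and so does a touch-up subject under the last-injection rule.

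Example, h = 4: f(4) = 0.721, f(8) = 0.541, f(12) = 0.421. Track A captures (4×0.721 + 8×0.541)/12 = 0.601, and 0.601/0.421 = 1.43.

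| h (weeks) | A, no touch-up | B | Ratio, no touch-up | Ratio, touch-up |
|---|---|---|---|---|
| 2 | 0.406 | 0.237 | 1.71 | 1.00 |
| 4 | 0.601 | 0.421 | 1.43 | 1.00 |
| 8 | 0.763 | 0.622 | 1.23 | 1.00 |
| 26 | 0.917 | 0.856 | 1.07 | 1.00 |
| 52 | 0.957 | 0.924 | 1.04 | 1.00 |

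**Self-reporting.** If half of AEs are reported whatever the schedule, the ratio without touch-up is (0.5 + 0.5×0.601)/(0.5 + 0.5×0.421) = 1.13 at h = 4 and 1.09 at h = 8.

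**Mixed touch-up.** The share with touch-up is not given. If it were half, averaging the two Track A captures gives ratios of about 1.36, 1.21 and 1.11 at h = 2, 4 and 8, with no self-reporting.

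**In subjects.** With 22 per track (45 at 1:1), an assumed true risk of 20% and h = 8, without touch-up or self-reporting: 22 × 0.20 × 0.763 = 3.4 against 22 × 0.20 × 0.622 = 2.7 expected.

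**What a Month 1 contact in Track B would do.** Track B's mean wait falls from 6.0 to 3.33 weeks, equal to Track A without touch-up. Touch-up subjects, if still asked at Weeks 4 and 16, would then be the less well-ascertained group: 0.237/0.406 = 0.58, 0.421/0.601 = 0.70 and 0.622/0.763 = 0.82 at h = 2, 4 and 8.

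**The case against.** A reader might infer that within the same 12 weeks every Track A subject is asked twice and every Track B subject once, and that the AE comparison is therefore biased. The documents do not support that. Four points count against it, and all four stand.

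- **Touch-up.** Asking twice in 12 weeks holds for all of Track A only under 10.3.2. Under the last-injection rule, a touch-up subject is asked once by Week 12, as in Track B, and the modelled ratio is 1.00. That equality is a cancellation, though: it needs even onset, and the two parts of the window remain misaligned in opposite directions.
- **Recall loss is assumed.** With half-lives of 26 or 52 weeks the ratio is near 1. Both tracks are told to report symptoms between visits, which shrinks it further. This provision does not close the gap, because the instructions concern unusual or unexpected symptoms, and minor ordinary events still depend on being asked.
- **Few events may be affected.** Section 11.1.2 keeps common filler reactions out of the AE record unless they are excessive and clinically significant. Injection-related events also cluster after treatment, so even onset is a simplification.
- **No AE test is planned.** Between-group testing is stated under efficacy (12.2) and is exploratory. The study objective concerns the sequential regimen, and only the design sentence in Section 3 frames safety as one regimen against the other.

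The direction also matters. Where the imbalance applies, it overstates the apparent Bellafill excess and does not hide a Bellafill risk. Adding a Track B contact alone would reverse that for touch-up subjects, so the fix must go further.

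**Conclusion.** The scheduled asymmetry is a fact: Track A has an AE and concomitant-treatment assessment at Month 1, and Track B has nothing scheduled until about Week 12. That it may under-ascertain short, unreported AEs in Track B is a reasonable inference; that it does so is not shown.

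Over Weeks 0-12 the net imbalance applies to Track A subjects without touch-up, or to all of Track A if 6a is timed from Visit 4. Its size rests on assumed recall loss, even onset and the extent of self-reporting. It runs from 1.71 at a 2-week half-life down to 1.04 at 52 weeks with no self-reporting, and is about 1.1 at 4 to 8 weeks if half of AEs are self-reported. In the worked case, the difference is less than one expected subject.

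The effect falls on tabulated incidence, not on a planned test. This is a minor point, but worth acting on: events that were never asked about cannot be recovered at analysis, and the remedy is cheap.

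**What to change.** 1. Add to the schedule in 10.1 and to 10.4 a telephone or e-mail contact for Track B at Month 1 (±1 week, counted from Visit 4), covering AEs and concomitant treatments and using the Section 9 opening question.
2. Reconcile the timing of 6a and 7a in 10.3.2 and 10.3.3 with the synopsis, Section 3, Section 3.1 and the footnote to 10.1.
3. If 6a stays tied to the last injection, add a Week 12 telephone or e-mail AE contact for touch-up subjects. Both tracks are then asked at Weeks 4 and 12, and the mean wait is 3.33 weeks in every group.
4. State in 12.3 that between-track AE tables use this common 12-week window from Visit 4. Later Track A events can be tabulated separately.

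The cost is about 22 short contacts in Track B and one per touch-up subject, made by existing site staff, plus a few lines in the schedule and analysis text. No treatment changes.
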